**SYNOPSIS**

Protocol Number	PCP 002
Title	A Randomized, Open-Label, Controlled, Multi-Center Study on the Efficacy of a Sustained Release Progesterone Cerclage Cervical Pessary at Doses of 6.3 g or 7.7 g for the Prevention of Preterm Birth and a Maximum Duration of 20 Weeks
Sponsor and Phase	Andrómaco - Phase II
Type of Investigation	Medical Device
Type of Study	Interventional
Study location	1. Instituto de Investigación Materno Infantil (IDIMI) – Maternidad Hospital Clínico San Borja Arriarán (HCSBA). 2. UNICERH, South Department of Obstetrics & Gynecology – School of Medicine UCH Hospital Barros Luco 3. Centro de Investigación e Innovación en Medicina Materno Fetal (CIMAF) - Complejo Asistencial [name] del Río (CASR) . 4. East Department of Obstetrics & Gynecology – School of Medicine UCH Hospital [name] Brousse .
Primary Objective of the Study	To assess the efficacy of Cerclage Pessaries containing 6.3 g or 7.7 g of micronized progesterone for the Prevention of Preterm Birth, established through spontaneous parturition before gestation weeks 32 (31 6/7) and 34 (33 6/7), when the pessary is inserted between weeks 16 and 24 and removed at 36 6/7 weeks of gestation in pregnant women at risk of preterm birth.
Secondary Objectives of the Study	
 
• To record the occurrence of premature rupture of membranes before gestation weeks 32 (31 6/7) and 34 (33 6/7).
 
• To assess anatomical cervix features in pregnant women: position and length.
 
• To establish the acceptability and tolerance of the use of the Cerclage Pessary by pregnant women.
 
• To evaluate local and systemic safety in pregnant women using the Cerclage Pessary.
 

Study Design	Randomized, open-label, controlled clinical study of efficacy.
Study population	Voluntary patients:
Inclusion Criteria	
 
1. Women with single pregnancy and a cervical length of 10 mm - 25 mm between 16 and 24 weeks of gestation, without any previous risk factors.
 
2. Women with single pregnancy and a cervical length <math>\geq</math> 10 mm between 16 and 24 weeks of gestation, and pre-existing risk factors for preterm birth: 
 
• Previous preterm birth before week 35.
 
• Previous rupture of membranes before week 35.
 
 
 

Exclusion Criteria	
 
1. Pregnancies with: 
 
• Major fetal abnormalities, such as lethal malformations or malformations requiring pre- or post-natal surgery, and fetal death before randomization.
 
• History of rupture of membranes or prophylactic
 
 
 

	cerclage in the current pregnancy before inclusion into the study.
Planned number of participants	
2. Cervical or vaginal injuries prior to insertion of the pessary (e.g. cervical erosion secondary to trauma, infection or carcinoma, vesicovaginal or rectovaginal fistulas).
 
3. Unconscious, severely ill, mentally disabled patients, or under 16 years of age.
 
4. Patients for whom use of progesterone is contraindicated.
 
5. Patients with history of thrombosis.
 
A sample consisting of 270 pregnant women at risk of preterm birth, with useful information for the analysis and recruited in the 4 participating sites. This population will be divided into 3 groups of treatment, with 90 participants each.
 
The 3 groups of the clinical trial are: One control group with progesterone 200 mg vaginal capsules and 2 study groups with 2 different doses of progesterone in the pessaries.

Investigational Product	Cerclage pessaries containing 6.3 g or 7.7 g of sustained-release micronized progesterone each.
Outcomes to be evaluated	
Primary	Determination of the effective dose of progesterone in the cerclage pessary through the occurrence of spontaneous birth before 32 (31 6/7) and 34 (33 6/7) weeks of gestation.
Secondary	
Occurrence of rupture of membranes: Premature rupture of membranes before 32 (31 6/7) and 34 (33 6/7) weeks of gestation.
 
Cervical anatomic changes
 
 
1. Cervical length and internal cervical os dilation before and after inserting the pessary.
 
2. Cervical position in relation to the uterus longitudinal axis before and after inserting the medicated pessary.
 
 
Acceptability:
 
 
1. Ease of insertion
 
2. Pain of the patient at the time of insertion
 
3. Assessment based on the VAS during use
 
4. Spontaneous expulsion of the pessary
 
5. Request for early removal of the pessary
 
6. Subjective changes of vaginal discharge
 
 
Local safety: Major maternal complications attributable to the pessary (chorioamnionitis, severe vaginal or cervical trauma).

Length of the Study	21 – 48 months

## 2 RATIONALE

Nowadays, prematurity is a central issue both for obstetrics as well as for public health worldwide, as it is a highly incident clinical situation (affecting approximately 7% to 10% of births), and is involved in around 50 - 75% of neonatal morbidities and mortalities, mainly in neonates born before 32 weeks of gestation. Sequelae in premature neonates also impact on the increase of healthcare costs and infant mortality during the first year of life (1).

The rate of preterm births has not declined over the last 20 years, and in most developed countries it remains high despite advances in the knowledge about risk factors and mechanisms related to preterm births (2). Essentially, there are two reasons that explain the failure to reduce preterm births: first, the absence of a screening method effective for the identification of women at high risk for this event; and second, the lack of effective intervention to prevent this complication.

The most commonly adopted approach for identification of pregnancies at high risk for preterm birth has been the use of obstetrical history and mother's demographics.

In published screening studies where over 60,000 women with single pregnancies were included, the preterm birth rate by week 34 in England was 1.8%, very similar to that found in our country (1.3%). Preterm births were spontaneous in two-thirds of the cases (1.2% of the total), whereas one-third were iatrogenic. Only in 3% of cases, the patients had a history of preterm birth and this group accounted for 15% of the total number of spontaneous deliveries by week 34 only. This demonstrates that identification of patients at risk of delivery before week 34 based on obstetric history leaves most of these patients outside of the risk group, and therefore, not covered by preventive measures.

An effective method for prenatal screening to detect the risk of preterm birth is the measurement of the cervical length by ultrasound between gestation weeks 20 and 25. The risk of preterm birth both for single-fetus as well as for twin pregnancies is inversely related to the cervical length. Therefore, a woman with a cervical length (CL) between 1-10 mm has a risk of preterm birth of 44%, whereas a woman with a CL between 26-30 mm has a risk of 1.3%. The group with cervix measures of 1 to 15 mm corresponded to 28% of all spontaneous deliveries before week 34, and the group with a cervix measure of 16 to 25 mm corresponded to 21% (3).

In addition to the myriad of scientific evidence available from the studies above, they allow to state that the lower a certain cervical length in the second trimester of pregnancy, the higher the risk of spontaneous preterm birth both in single and twin pregnancies (4). However, there is still no consensus on the accurate definition for "short cervix" during gestation related to preterm birth risk prediction. Almost every women before 14 weeks of gestation including those at increased risk of preterm birth will have a normal cervical length (CL). A CL of 25 mm at this gestational age is only seen in women with a history of miscarriage in the second trimester, or who have undergone cervical surgery (cone). A CL in the range of 25-50 mm is normal between 14 and 24 weeks in all pregnant women. In women at low risk of preterm birth, the mean CL between 14-30 weeks of gestation is 35-40 mm, and the 10th percentile is 25 mm, while the 90th percentile lies in 50 mm. The optimal timing for measurement of the CL by transvaginal ultrasound should be accurately established since, if performed before 14 weeks, a separate visualization of the cervix from the lower uterine segment may be very difficult. In addition, after week 30, the cervix is

progressively shortened in preparation for a full-term delivery, so in asymptomatic women, a CL <25 mm after 30 weeks is physiological and indicative of a non-preterm birth (5).

Most women who have a preterm birth display a shortened neck for the first time approximately between 18-22 weeks of gestation, so the initial examination should be conducted at least within that period. Besides the already established inverse relationship between CL and the risk of preterm birth, the earlier the cervix is shortened during gestation, the higher the likelihood of a preterm birth. In women at higher risk, a CL <25 mm has a positive predictive value of 70% for preterm birth before 35 weeks when detected at 14-18 weeks, and 40% when detected at 18-22 weeks (5). In the same line of evidence, Vaisbuch *et al.* (4) recently demonstrated an approximate two-fold risk of delivery before 28 or 32 weeks if CL is  $\leq 15$  mm before 20 weeks (76.9% and 80.8%) versus 20-24 weeks (30.9% and 48.1%). Overall, this evidence suggests that starting the screening of patients with cervix measurements earlier than week 18 and using a 25-mm CL limit to determine the need for an intervention as discussed in this clinical study might entail a greater advantage.

### **Preventing the Preterm Birth**

The traditional practice for prevention of preterm birth is the administration of tocolytics to patients threatened to, or into premature labor. Although tocolytics administration has been used for several decades, systematic reviews of randomized studies have reported no improvement in the neonatal outcome with the administration of such agents or a decrease in the frequency of preterm births (7). Prophylactic administration of progesterone to women with a history of preterm birth and to those with short cervix and single-fetus pregnancy in mid-gestation has shown to significantly reduce the rate of spontaneous preterm birth (about 40-45% less) before week 33-34. However, there are 55-60% of patients remaining with shortened cervix who likewise and despite progesterone administration, gave birth by week 34 (8-10), which is in line with the multi-causal nature of this condition in humans.

Progesterone mechanism of action to prevent preterm births seems to be related in part with a local anti-inflammatory effect that stops or slows-down the pathway of biochemical events involved in cervical maturation and, on the other hand, by means of a mild inhibitory effect of uterine contractions (13).

The cervical cerclage surgical procedure has also been proposed as a prevention alternative in pregnant patients with single-fetus and short cervix. However, results in patients without previous history of cervical incompetence are still controversial. A recent publication shows that results in the prevention of preterm birth using cerclage for the indication of short cervix are similar in the group in which cerclage is indicated on the basis of the obstetric history. Thus, there would not be a rationale for expecting the cervical shortening to occur in order to perform the procedure (14). On the other hand, multiple observational studies and a recent randomized clinical study in patients with short cervix before 24 weeks of gestation show that the placement of a cerclage pessary (without surgery) significantly reduces the risk of preterm birth as compared to control patients (15-17). Previous evidence suggests that a mechanical factor—probably a cervical distension and/or pressure on the inner cervical os—seems to be also related to early cervical maturity and the risk of preterm birth.

Under normal conditions, an immature cervix in a pregnant woman is displaced posteriorly toward the sacrum, whereby the intrauterine and fetal presentation pressure are exerted on the uterine segment and not on the inner cervical os

(18), thus preventing early dilatation.

### **Cerclage Pessary without Drug Substance**

The cerclage pessary mechanism of action in the prevention of preterm birth has not been fully elucidated. Theoretically, the effect of the pessary is based on its mechanical capability to displace the cervix posteriorly, hence slightly increasing the cervix length and changing the angle of the cervical uterus. All these variations not only reinforce the cervical canal, but also reduce the likelihood for membranes to make contact with the vaginal environment, thus contributing to preserve its integrity (20). An additional benefit of the cerclage pessary may be that it contributes to maintain the immunological barrier between the extraovular chorio-amniotic space and the microbiology flora in the vagina—a mechanism similar to that postulated for surgical cerclage.

[REDACTED]

[REDACTED] In a paired-analysis, retrospective study on women with twin pregnancies and a cervical length below the 10th percentile by routine ultrasound, 23 cases were treated with the pessary and 23 received expectant management. The spontaneous delivery rate before week 32 was 0% in the group with pessary and 30% in the control group ( $p < 0.001$ ). In the same study, 12 women with single pregnancies were treated with the pessary and other 12 were treated with expectant management. The spontaneous preterm birth rate before week 36 was 0% in the group with pessary and 50% in the control group ( $p < 0.001$ ) (16). There are many other observational or case-control studies about the use of pessaries for preventing preterm birth. These studies date back to 1959 and have resulted in a promising absence of severe adverse effects (23).

A recent study that included 385 patients with single-fetus pregnancies and shortened cervix confirms the findings above, even though the magnitude of reduction in the prematurity rate for the control group appears to be disproportionately high (17, 20).

[REDACTED]

### **Development of a Cerclage Pessary containing Sustained-Release Progesterone**

[REDACTED]

[REDACTED]

[REDACTED]

[REDACTED]

[REDACTED]

On the basis of the same principle, the development of a cerclage pessary containing progesterone, which is released in a sustained manner upon implantation around the cervix, has been initiated.

[REDACTED]

### **Characteristics of the Cerclage Pessary with Sustained-Release Progesterone**

[REDACTED]

[REDACTED]

### **3 STUDY OBJECTIVES**

**Primary Objective:** This is a Phase II clinical study to assess the efficacy of two cerclage pessaries containing 6.3 g and 7.7 g of sustained-release micronized progesterone for the prevention of preterm birth, established by spontaneous delivery before gestation weeks 32 (31 6/7) and 34 (33 6/7) when the pessary is inserted between weeks 16 and 24 and removed in gestation week 36 6/7, in pregnant women at risk of preterm birth.

**Secondary Objectives:**

- To record occurrence of premature rupture of membranes before gestation weeks 32 and 34.
- To assess anatomical cervix features in pregnant women: position and length.
- To establish acceptability and tolerance in pregnant women using the Cerclage Pessary.
- To evaluate local and systemic safety in pregnant women using the Cerclage Pessary.

## 4 STUDY DESIGN

The study will be conducted in compliance with the protocol, the good clinical practice standards, and the provisions of the corresponding ethics committee.

This will be a randomized, open-label, controlled, multicenter, exploratory Phase II study of efficacy. Pregnant patients with a single fetus who after reading the informed consent voluntarily agree to participate in the study will be included.

For secondary outcomes, patients will be their own controls on the following endpoints to be tested: cervix anatomical features—position and length—; plasma and endometrial progesterone concentrations in non-pregnant menopausal women; surveys on pregnant women to establish the acceptability and tolerance of the intervention; and local and systemic safety issues.

4.1. Pregnant Volunteers: 270 + 10% pregnant women at risk of preterm birth from the 4 participating sites will be recruited. This population will be divided into 3 treatment groups with 90 participants each.

They will be informed and invited to participate in the study at prenatal and/or ultrasound control between 16 and 24 weeks of gestation. Volunteers will be included in all cases up to 24 (0/0) weeks of gestation. Volunteers will be selected on the basis of their clinical history and by transvaginal ultrasound performed between weeks 16 and 24. All volunteers with a single pregnancy and cervical length  $\leq 25$  mm but  $\geq 10$  mm will be invited to participate in the study. Prior to inclusion in the study, fetal vitality or other exclusion factors discussed in detail below will be confirmed. Those patients who do not agree to participate in the study will receive the current standard care at each participating site depending on their condition.

4.1.1. Inclusion criteria in pregnant volunteers:

- Pregnant women with a single fetus with a cervical length of 10-25 mm between 16 and 24 weeks of gestation with no pre-existing risk factors.
- Women with ongoing pregnancy between 16 and 24 weeks of gestation with a single fetus and cervical length  $\geq 10$  mm, and having pre-existing risk factors in the immediately previous pregnancy characterized by:
  - Preterm birth before week 35 (with a viable fetus).
  - Premature rupture of membranes before week 35 (with a viable fetus).

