## 5 PROCEDURES

### 5.1. Recruitment and Screening

Patients will participate voluntarily and under informed consent. Participant selection will be performed by screening the general population of pregnant women with single fetus monitored by the Hospital Healthcare Network, to investigate by serial transvaginal ultrasound performed between gestation weeks 16 (0/7) and 24 (0/7) those patients who have a cervical length between 10 mm and 25 mm, and/or women with a single fetus and cervical length  $\geq 10$  mm presenting one or more of the following risk factors: a) preterm birth prior to 35 (34 6/7) weeks of gestation; b) premature rupture of membranes prior to 35 (34 6/7) weeks of gestation.

Gestational age will be determined by the last menstruation date and will be confirmed by measurement of the craniocaudal length obtained in the first trimester ultrasound, or by measurement of the cephalic circumference in the second trimester ultrasound predominating the actual date of the last menstrual period (LMPad).

The selected volunteers will be examined and those with vaginal discharge will undergo clinical examination and/or bacteriological investigation and if confirmed for infection, this will be treated with the appropriate antibiotic. In these cases, insertion of the sustained-release progesterone cerclage pessary will be performed subsequent to the end of treatment although before 24 (0/1) weeks of gestation.

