#### 5.4. Intervention and follow-up

The intervention and follow-up of participants will begin after the conditions eligible to participate in the study are verified, proceeding as follows:

5.4.1. For selected participants with pre-existing risk factors, these are: immediately previous pregnancy terminated prematurely with preterm birth, or premature rupture of membranes before 35 weeks of gestation; placement of a progesterone cerclage pessary, or treatment with progesterone capsules will start at week 16 (0/7) but not beyond 24 (0/7) weeks of gestation. These participants will have a transvaginal ultrasound performed to document the length ( $\geq 10$  mm) and position of the cervix at the placement of the pessary or the start of treatment with vaginal progesterone capsules.

5.4.2. For pregnant patients with a single fetus, selected for the presence of a shortened cervix (between 10 mm and 25 mm), the pessary will be inserted or the vaginal administration of progesterone capsules will be started at the time of the investigation, but not before 16 (0/7) weeks of gestation and not after 24 (0/7) weeks of gestation. The cervix angulation relative to the uterus body using the intersection of the uterus posterior wall longitudinal axis with the cervical canal axis in addition to a measurement of the cervical length will be performed on 60% of the study participants assigned to one of the two groups with medicated pessary, prior to insertion of the pessary and after its insertion, by means of a transvaginal ultrasound technique recently described (25). The transvaginal ultrasonography post-insertion of the pessaries may be performed at visit one or at visit two at the latest.

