3. STUDY DESIGN

A phase II, efficacy, multicenter, controlled, open label, parallel and randomized exploratory clinical study. It will include singleton pregnant subjects, with history of premature birth and/or short neck and an increased risk of premature birth, who, after reading the informed consent, voluntarily accepted to participate in the study.

For the secondary outcomes, subjects will be their own controls on the following variables to assess: anatomical characteristics of the cervix – position and length; development of surveys in pregnant women to establish the acceptability and tolerance of the intervention; and aspects of local and systemic safety.

Two hundred and seventy +10% pregnant women with risk of premature birth will be enrolled at the participating sites. This population will be divided into 3 groups of treatment with 90 participants each, where control group (A) is with intravaginal capsule of micronized progesterone 200 mg, groups B and C are pessaries with 6.3 g and 7.7 g of sustained release progesterone respectively.

In the prenatal and/or ultrasound control between 16 and 24 weeks of gestation, they will be informed and invited to participate in the study. The inclusion of the volunteers will be in all cases until weeks 24 (0/0) of gestation. The volunteers will be selected on the basis of their clinical history and by trans-vaginal ultrasound performed between 16 and 24 weeks. All volunteers with unique pregnancy and cervical length ≤ 25 mm but ≥ 10 mm, will be invited to participate in the study. Prior to inclusion in the study, it is confirmed the vitality of the fetus or other exclusion criteria detailed later. Subjects who refuse to participate in the study will receive the current standard of care in each participating site, according to their condition.

EVALUATION VISITS

The study includes 8 visits to the site. The programmed schedule of assessments for its conduction and the activities to take place in each and one of them are specified in Table 1.

SAMPLE SIZE

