6. POPULATION DEFINITIONS

In order to meet the needs of the sub-groups of the Protocol, the following population sub-groups are defined:

Per Protocol (PP): It is defined as the subset of participants who meet the criteria of selection, who expressed their desire to participate in the study, who signed the informed consent form, that the drug has been administered to them and have completed all the visits required or till the termination of the pregnancy as per Protocol.

Intention to treat (ITT): It is defined as the subset of participants who meet the selection criteria, showing their desire to participate in the study, who signed the informed consent form, that the drug has been administered to them, who have at least completed the initial visit and at least one of the subsequent visits to the pessary referred to in the Protocol.

The main efficacy analysis will be carried out with a focus Per Protocol (PP), however it will also be carried out per Intention to Treat (ITT) all the analysis. Otherwise, the main safety analysis will be completed as ITT.

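### The obstetric-history entry criterion has three wordings, and both SAP analysis sets depend on meeting it, so a woman randomised under the broader wording can be removed from both sets

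*Protocol*

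**What the plan says.** The history route into the trial is described in several places.

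- **Protocol, Synopsis:** "Previous preterm birth before week 35" or "Previous rupture of membranes before week 35". There is no limit on which pregnancy and no viability condition.
- **Protocol 5.1 (screening):** women "presenting one or more of the following risk factors: a) preterm birth prior to 35 (34 6/7) weeks of gestation", with membrane rupture before the same limit as factor b). Again neither restriction appears.
- **Protocol 5.4.1 (start of treatment):** "immediately previous pregnancy terminated prematurely with preterm birth, or premature rupture of membranes before 35 weeks of gestation". The pregnancy is restricted; viability is not mentioned.
- **Protocol 4.1.1 (inclusion criteria):** "having pre-existing risk factors in the immediately previous pregnancy characterized by" events that also carry a viability condition ("Preterm birth before week 35 (with a viable fetus").
- **SAP:** sections 8 and 10 repeat the 4.1.1 version. Section 3 speaks only of a history of premature birth, without qualification.

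SAP section 6 defines the ITT set as "the subset of participants who meet the selection criteria", with further conditions on dosing and visits. The per-protocol (PP) set has an equivalent eligibility condition. PP carries the main efficacy analysis, with ITT run alongside it. The main safety analysis uses ITT. No set of all randomised women is defined.

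**The concern.** Differences in wording would matter little if every randomised woman were analysed. Here membership of both analysis sets depends on the criterion whose wording differs. A site following section 5.1 can properly randomise a woman who fails section 4.1.1. When the sets are formed, someone must choose which text governs her, and the SAP gives no rule.

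The trial is open-label, so that choice can be made with her arm, and possibly her outcome, known. If she is removed, she leaves the main efficacy analysis and the ITT analysis that should act as the check on it. The benefit of randomisation is then lost for her in both. The four sites could also screen to different rules.

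**Working it through.** This is a comparison of texts. The plan gives no figure for the number of women affected.

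**Step 1. Apply each wording to the same woman.** All have a singleton pregnancy at 16 to 24 weeks.

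| Woman | Synopsis, 5.1 | 5.4.1 | 4.1.1, SAP 10 |
|---|---|---|---|
| Cervix > 25 mm; event in last pregnancy, viable fetus | in | in | in |
| Cervix > 25 mm; event in last pregnancy, fetus not viable | in | in | out |
| Cervix > 25 mm; event only in a pregnancy before the last | in | out | out |
| Cervix 10-25 mm; event only in a pregnancy before the last, or not viable | in | in through 5.4.2 (short cervix) | unclear |

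The last cell is unclear because the short-cervix route in 4.1.1 is for women without pre-existing risk factors. If that term means only the listed factors, she has none and enters by cervical length. If it has its ordinary meaning, she fits neither route.

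**Step 2. Direction.** For the history route, 4.1.1 is contained in 5.4.1, which is contained in 5.1 and the synopsis. The risk therefore runs only from broad to narrow.

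**Step 3. Look for a rule that settles it.**

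- SAP section 1 makes the protocol the final reference, but the conflict lies within the protocol.
- Protocol 5.5 to 5.7 keep women in the analysis after unreplaced expulsion, poor adherence or pessary removal. None covers a woman later judged ineligible.
- SAP section 7 lists failure of entry criteria among the discontinuations. Protocol 5.4.3 has visits record possible causes of exclusion after the fact, without defining them.

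Nothing retains her, and two passages contemplate exclusion.

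**Step 4. Illustrative size.** Assume that 2% to 10% of women are affected; the documents give no share.

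- All arms: 270 × 0.02 = 5.4 to 270 × 0.10 = 27.
- Per arm: 90 × 0.02 = 1.8 to 90 × 0.10 = 9.

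For power, use the two-sided, uncorrected test at 0.05 with n per arm:

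power = Φ{ [ |p1 − p2|√n − 1.96√(2p̄(1 − p̄)) ] / √[p1(1 − p1) + p2(1 − p2)] }, where p̄ = (p1 + p2)/2.

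The plan states at least 80% power with 90 per arm but gives no control rate. Two assumed pairs are consistent with it: 0.51 v 0.306 (a 40% relative reduction), power 0.80; and 0.40 v 0.20, power 0.84. Enrolment is 90 × 1.1 = 99 per arm, and a 10% loss leaves 99 × 0.9 = 89.1.

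| Further excluded | n per arm | Power, 0.51 v 0.306 | Power, 0.40 v 0.20 |
|---|---|---|---|
| 0% | 89.1 | 0.796 | 0.836 |
| 2% | 87.3 | 0.788 | 0.828 |
| 10% | 80.2 | 0.753 | 0.795 |

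Even at 10%, power falls by only about 4 percentage points. The concern is selection after randomisation, not precision.

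**The case against.** The best defence is that only 4.1.1 is headed as inclusion criteria. The synopsis is a summary, and 5.1 describes screening of a general population. Section 5.4 starts treatment only once eligibility is verified, and 5.4.1 repeats the restriction to the last pregnancy. SAP section 8 describes the history item in the narrow form. Obstetric history and eligibility are Visit 1 items, fixed before randomisation, so there is less room for biased judgement than with adherence or outcome. On this view 5.1 is the one operative outlier and few women are affected.

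Much of this stands. It makes the narrow reading more likely and the number small. It does not remove the conflict: 5.1 sets out the groups to be selected at screening, and 5.4.1 differs from 4.1.1 on viability. The history is fixed, but the choice of text to judge it by is not.

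A reader might also infer that only women with a cervix of 10 to 25 mm may be invited, which would contradict the history route. The documents do not say that. SAP section 3, like Protocol 4.1, says "All volunteers with unique pregnancy and cervical length" in that range will be invited, and the sentence before it also selects on clinical history. The invitation sentence omits the history route; it does not close it.

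**Conclusion.** The point holds as an internal inconsistency with a consequence for the analysis. Three wordings coexist, both analysis sets depend on the criterion, and no rule says which wording governs. Removal of a randomised woman from PP and ITT is possible, not certain. Those clearly exposed have a cervix above 25 mm and a qualifying event only in a non-immediate or non-viable pregnancy. Women with a 10 to 25 mm cervix and such a history are uncertain.

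Three stronger readings are not supported:

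- **That women entered under either wording can be dropped under the other.** The wordings are nested, so a woman who meets 4.1.1 meets them all.
- **That the SAP follows 4.1.1 throughout.** Sections 8 and 10 do; section 3 does not.
- **That the women at stake rival one arm's expected events.** That would set women from three arms against events in one, using an event rate found in neither document. If a rate of 15% to 20% is assumed, one arm of 90 has 90 × 0.15 = 13.5 to 90 × 0.20 = 18 events. Even 27 affected women at 20% would have 27 × 0.20 = 5.4 events over three arms, or 1.8 per arm.

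The number affected is unknown and probably small. The change is worth making because it is nearly free and corrects a stated rule that can remove randomised women from the ITT set.

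**What to change.** 1. **Reconcile the criterion.** Use one wording in the Protocol synopsis, 4.1.1, 5.1 and 5.4.1 and in SAP sections 3, 8 and 10. Which wording is the sponsor's clinical decision. Say whether a history outside it counts as a pre-existing risk factor for the short-cervix route.
2. **Complete the invitation sentence** in Protocol 4.1 and SAP section 3 by adding the history route.
3. **ITT, SAP section 6.** Remove the selection-criteria condition. State that an eligibility failure found after randomisation is flagged as a deviation and does not remove a woman from ITT.
4. **PP, SAP section 6.** ITT alone is not enough, because PP carries the main efficacy analysis. State that a woman who met any of the history wordings in the protocol version in force at her enrolment is not excluded from PP on this ground.

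The cost is a text amendment to both documents and a short notice to the four sites. If the protocol change counts as substantial, section 12 requires ethics committee approval first. No new data, visits or participants are needed.
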